# APPLICATION & PROTOCOL

cycle.				
Food Allergens: Ingredient lists and packaged foods with clearly labeled allergen information will be provided to subjects upon request. Subjects will be asked to notify the study nurse of any food allergies before ordering breakfast.				
Foodborne illness: Subjects will be instructed to store Brussels sprouts frozen and only thaw immediately before consumption. Study team members handling the Brussels sprouts will have Oregon Food Handler's Licenses, and the study Brussels sprouts will be repackaged in a facility compliant with Oregon Health Authority, Division 150, Food Sanitation Rule.				
Confidentiality/anonymity: Protection efforts are described in the Privacy and confidentiality section				
	Consider whether it is appropriate to provide participants with contact information for one or more resources during the recruitment or consent process (e.g., CAPS if OSU students, EAP if OSU employees, suicide prevention hotlines, address of local shelters, etc.).			
5	If the study is greater than minimal risk, attach a Data and Safety Monitoring Plan or provide the following information:			 Skip to section 38
5a	Definition of an adverse event for this study:			
	DSMP is attached			
5b	Definition of a serious adverse event for this study:			
	Provide a plan for managing adverse events:			
	Summarize any reporting requirements and timelines:			
	Indicate if there are any individual or overall study stopping rules:			
	Provide the plan for reporting adverse events or unanticipated problems (e.g., breach of confidentiality, incarcerated participant, or an unresolved complaint):			
	If the potential harm related to physical, psychological, or financial risks is greater than minimal, describe			

# APPLICATION & PROTOCOL

	the plan for paying for related costs to participants:			
	NIH guidance on data and safety monitoring			
SECTION 38 - Benefits		Yes	No	N/A
1	Describe benefits to the individual participants, to society, and to science:  This study is not designed to be of benefit to individual subjects. Potential benefits to society include essential information to aid regulatory agencies with respect to how environmental PAHs, such as BaP, at environmentally relevant levels of exposure are taken up by the G.I. (96% of carcinogenic PAH exposure in humans is dietary), metabolized and excreted from the body. That information can be used in modeling risk assessment rather than high-dose animal studies. This will provide a mechanism for improvement of public health.			
SECTION 39 - Training and Oversight		Yes	No	N/A
	CITI training is required and should not be included in this section. This section pertains to all other training required to conduct the study, such as training study team members to collect data or samples.			
1	Is the PI the only member of the study team?			
2	Describe the plan for confirming or providing training related specifically to the study activities and for supervising all study team members:  [name] is responsible for the conduct and oversight of the study, for ensuring that privacy/confidentiality of subjects is maintained and that all individuals working on the study are properly trained to perform their role on the study.			
3	Describe the plan for training related specifically to obtaining informed consent and maintaining confidentiality:  Nurse coordinator [name] will obtain informed consent from study subjects. She has completed a clinical research coordinator (CRC) training course and will be responsible for maintaining confidentiality.			
4	Explain how oversight of study team members will be handled during PI absences (sabbaticals, non-contract months, etc.):  Extended absence of the PI is not anticipated because the PI will not use sabbatical leave during the study, is appointed at 1.0 FTE (9-month) and a tenured faculty member. A certified phlebotomist may occasionally be employed to collect blood samples as a back-up to [name].			

 Assent document(s) or guide(s)  Certificate of Analysis or other documentation of quality/purity  Certificate of Confidentiality  CLIA certificate  Consent document(s) or guide(s)  Copy of curriculum if the study intervention is a workshop or a class  Data and Safety Monitoring Board Charter or Report				

# APPLICATION & PROTOCOL

 Data and Safety Monitoring Plan
 Department of Corrections application
 Documentation that the product is an approved food additive (21 CFR 172)
 External IRB document(s)
 External study document(s)
 FDA Correspondence
 FDA "Safe to Proceed" letter
 GMP certificate or food-grade certificate that indicates that the product can be lawfully used in the US food supply
 Grant or contract if not already in Cayuse
 IND or IDE Application for Investigational New Drug or Device
 Investigator brochure
 Label for investigational drug or device
 Letter from the FDA or industry sponsor setting forth the IND number
 Letter(s) of support or permission
 Package insert
 Recruitment materials
 References or citations
 Safety data if GRAS status is self-affirmed
 Screening or eligibility checklist(s) or document(s)
 Surveys, questionnaires, interview or focus group guide(s)
 Translated document(s)
 Tribal Council Resolution or other appropriate supporting documentation from the appropriate Tribal authority

**Additional attachments:**

 Food diary
 Demographics form
 Cruciferous vegetable list
 Health assessment form
 Cruciferous vegetable food frequency questionnaire (FFQ)
 BioResponse DIM 150 label
 Brussels sprouts preparation instructions

## APPLICATION & PROTOCOL

**PI should email completed application and all relevant attachments to [contact]**

## Statistical Analysis Plan

Pharmacokinetic parameters were evaluated for linearity using a best fit modeling approach. First, pharmacokinetic parameters were evaluated for significant change as a function of dose using a standard linear regression model including a fit y-intercept. Slopes were compared using a *t*-test and an alpha value of 0.05. If the parameter changed as a function of dose, we further evaluated the parameter with a linear regression model, with *k* as the slope through the origin and a Michaelis-Menten model, which assumes saturation at  $V_{max}$  and an affinity constant *K*, to individual parameters (*p*) as a function of external [ $^{14}\text{C}$ ]-BaP dose. The Bayesian information criterion (BIC) was used to judge the best-fit model and provide evidence of linear or saturable pharmacokinetics.

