Our hypothesis is that pre-administration of Brussels sprouts or 3,3'-diindolylmethane (DIM) will alter [C]-BaP metabolism and increase the rate of elimination consistent with predictions based on a previously developed Physiologically-Based Pharmacokinetic (PBPK) model for BaP. Briefly, this hypothesis will be tested by dosing individuals with 50 ng [C]-BaP alone and, following a 3-week washout period, ingestion of ½ cup (about 44 g) Brussels sprouts or 300 mg of 3,3'-diindolylmethane (DIM) supplement for 1 week prior to the [C]-BaP micro-dose. The impact of the supplement and the whole food will be assessed with respect to alterations in uptake from the GI tract, metabolism and rate of elimination. To date, our accelerator mass spectrometry (AMS) studies with PAHs have not investigated the impact of diet on [C]-BaP pharmacokinetics. The consumption of cruciferous vegetables will be assessed at the beginning of the study by completion of a dietary questionnaire to examine typical eating patterns in the previous 3 months and by collection and extraction of blood and urine to assay for DIM by LC/ESI-MS/MS-SRM. In addition, for each phase, urine will be assayed for DIM as an estimate of crucifer or DIM supplement intake. [C]-BaP and metabolites will be extracted from plasma and urine (with and without  $\beta$ -glucuronidase/sulfatase) and shipped to Lawrence Livermore National Laboratory (LLNL) for UPLC-AMS analysis. The PK parameters will be assessed at PNNL and the impact of Brussels sprout or DIM consumption on uptake, metabolism and elimination of [C]-BaP determined. In preclinical and clinical studies administration of Brussels sprouts or DIM impacts the activity of the same enzymes responsible for the phase 1 (CYP1A1 and CYP1B1) and phase 2 enzymes (GSTM1, UGT, SULT). Monitoring changes in  $\beta$ -estradiol metabolites will confirm the mechanism of alteration in the metabolic profile of [C]-BaP.

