# APPLICATION & PROTOCOL

	results are expected to fill. Summarize relevant existing data, literature, past and ongoing studies, and how your study ties in with these.  Provide specific methods and procedures in a later section.			
4	Is the study student-driven (for the purpose of a thesis, dissertation, or other)?			
SECTION 14 - Target Enrollment				
1	What is the target enrollment number?			
	Up to 50 people will be enrolled in this study. Our goal is for 7 subjects to complete the study.			
	A target enrollment number is not applicable for studies limited to chart review or review of large, pre-existing datasets, such as those originating from public health surveillance organizations.			
	If the study is determined to be exempt, expedited, or eligible for flexibility in the application of the regulations, an approximate number is sufficient for the evaluation of risk. The PI will not be required to report enrollment numbers to the IRB over the course of the study. However, if the study involves more than minimal risk or is FDA-regulated, an exact number is required and cannot be exceeded without prior approval.			
	FAQ What is the “total target” enrollment number?			
2	Provide scientific justification for the target enrollment number:			
	We expect a high percentage of screen failure. If a large number of study enrollees qualify to participate in the study, we will stop enrolling subjects prior to reaching our maximum enrollment figure.			
SECTION 15 - Participant Demographics				
1	Age ranges	Check all that apply		
1a	0-7			
1b	8-17			
1c	18-89			
1d	90+			

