### Cycle 1: [C]-BaP capsule only

The IV catheter will be placed in an appropriate vein in the forearm or antecubital region by the nurse coordinator. Subjects will swallow a capsule containing the [C]-BaP with 100 mL water. Prior to micro-dosing with [C]-BaP, a time zero blood sample of 20 mL will be collected with 10 mL analyzed for background plasma levels of BaP (and 62 additional PAHs) with GC-MS/MS and the remaining 10 mL analyzed for [C]-BaP and metabolites as with subsequent time points.

Blood will be sampled at 0, 0.25 0.5, 1.0, 1.5, 2, 3, 4, 8, 24, and 48 hours (11 draws total, 8-9 of which come from the catheter). The catheter will remain in place for blood draws through hour 4. After the 4 hour blood draw, subjects will have the choice of having the catheter removed and returning for the 8 hour blood draw by straight stick, or they can keep the catheter in place and remain on-site until after the 8 hour blood draw. The subjects will be monitored by the nurse coordinator between blood draws. The 8 (possibly), 24, and 48 hour blood draws will be done with straight stick phlebotomy. No more than three (3) skin punctures will be made in an attempt to draw blood at each visit. The first blood draw of this cycle will be 20 mL and then subsequent blood draws will be 10 mL.

Subjects will be instructed to collect all urine during the entire 48-hour study cycle in containers provided by the study team.

Two hours after swallowing the capsule, a standardized breakfast will be provided, after which subjects may resume normal eating and drinking. Snacks or fluids will be provided prior to the standardized breakfast if the study team determines it is necessary.

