## APPLICATION & PROTOCOL

### **Cycles 2 and 3: [C]-BaP capsule with Brussels sprouts and [C]-BaP capsule with DIM**

Visit 0 (20 minutes): Seven days before the capsule is taken, subjects will come to the CRC for a spot urine collection (analyzed for DIM and β-estradiol metabolites) and 25 ml blood sample (analyzed for background BaP and 62 other PAHs, DIM, β-estradiol and metabolites.) They will pick up their study Brussels sprouts or DIM capsules as described below:

*Brussels sprouts:* Subjects will be provided 7 days' servings of frozen, pre-cooked Brussels sprouts. Each serving will be about 50 grams (about ½ cup) of frozen Brussels sprouts. Study team members will record serving weights before providing to subjects and serving weights will be standardized as much as possible. Subjects will be instructed to consume one serving with dinner (defrost, warm and season, if desired) during the 7 days prior to the study cycle.

*DIM capsules:* Subjects will be provided 7 days' worth of BioResponse DIM® 150 capsules. They will be instructed to take 2 capsules (300 mg total) each evening with dinner during the 7 days prior to the study cycle.

The IV catheter will be placed in an appropriate vein in the forearm or antecubital region by the nurse coordinator. Prior to micro-dosing with [C]-BaP, a time zero blood sample of 25 mL will be collected with 10 mL analyzed for background plasma levels of BaP (and 62 additional PAHs) with GC-MS/MS and the remaining 15 mL analyzed for DIM as well as β-estradiol and metabolites. Fifteen mL will be taken at the 48 hour time point to determine what changes may have occurred in blood and urine levels of DIM and estrogens. Subjects will swallow a capsule containing the [C]-BaP with 100 mL water. For the DIM study cycle, subjects will also take 2 capsules (300 mg BioResponse DIM®) with the [C]-BaP capsule.

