## APPLICATION & PROTOCOL

composed of vegetable cellulose, will be opened and held in a microtube rack. The empty capsules will be filled with lactose. The 25 µL aliquot of either stock solution will be applied to the lactose with a calibrated pipet fitted with a sterile filter tip. The ethanol is allowed to evaporate, and then the capsules are sealed with their caps.

Five (5) capsules will be prepared in each batch: Up to two (2) subjects may participate in a study cycle per week and three (3) capsules will be used for quality control verification.

Capsules for quality control: Immediately after preparation, 3 of the 5 capsules will each be dissolved in 5 ml ultrapure water and 15 ml scintillation cocktail and counted on a liquid scintillation counter. Results will be emailed directly to the director of OSU Radiation Safety (RSO). Once the RSO has determined that the three evaluated capsules are within 10% variance and 10% error, the results are emailed to [name] or [name]. [name] will then contact [name] and [name] that the cycle(s) may proceed. If the capsules are not given RSO approval, a new set of capsules will be prepared and the subject(s) will be rescheduled if needed.

Capsules for subjects: Two capsules will be stored in sealed vials in the dark in a zipper-lock plastic bag with silica desiccant at -20°C until subject consumption. The bag will be labeled appropriately (see sample label). Any capsules not used within 1 week will be discarded.

*Dispensing:* Capsules will be transported to the Clinical Research Center (407 LPSC) in sealed vials within the labeled zipper-lock plastic bag. The bag will be stored within a plastic box for transportation to the clinic.

One (1) capsule containing 50 ng [C]-BaP will be administered to the subject with 100 mL of water by the nurse coordinator at the start of the study cycle.

*Inventory control:* Information including number of capsules, date of preparation, and operator are recorded immediately after capsules are prepared. Date of consumption and disposal of test capsules are recorded on day 1 of the cycle. If test capsules do not pass approval by the OSU radiation safety officer, the information is still recorded and a new set of capsules will be prepared.

*Disposal:* Capsules that are not needed, expired or rejected for human use will be disposed of in the radiochemical dry waste at Oregon State University.

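### The SAP models PK parameters only against BaP dose, but every cycle gives 50 ng, and no comparison of BaP alone, sprouts and DIM is specified

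*Combined protocol and SAP*

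**What the plan says.** The Statistical Analysis Plan is a single paragraph about linearity. In its first step, "pharmacokinetic parameters were evaluated for significant change as a function of dose using a standard linear regression model including a fit y-intercept", with a t-test on slopes at 0.05. Only if a parameter changes with dose does a second step follow: a line through the origin and a Michaelis-Menten curve are fitted against external labelled BaP dose, and BIC picks between them. Sprouts, DIM, cycle, participant and pairing are not mentioned.

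The protocol asks a different question.

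- **Hypothesis** (Section 13, item 1): "Our hypothesis is that pre-administration of Brussels sprouts or 3,3'-diindolylmethane (DIM) will alter" BaP metabolism and speed its elimination, in line with an existing PBPK model. On method, the same item says only this: "The PK parameters will be assessed at PNNL and the impact of Brussels sprout or DIM consumption on uptake, metabolism and elimination of" labelled BaP is to be determined.
- **Conditions** (Section 20): three cycles per participant. The first is headed "Cycle 1: [ 14 C]-BaP capsule only"; the other two add a week of sprouts or of DIM, in no set order. Participants from protocols 8233 or 8554 skip the BaP-only cycle if they completed it at 50 ng within the prior 12 months.
- **Dose** (Section 24, items 7 and 17): 50 ng is the only strength listed. "One (1) capsule containing 50 ng" is given at the start of each cycle.
- **Capsule control** (Section 24, item 17): dosing may proceed once "the three evaluated capsules are within 10% variance and 10% error". Those three are dissolved for counting; no count of the swallowed capsules is described.
- **Size** (Section 14): "Our goal is for 7 subjects to complete the study".

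**The concern.** The SAP regresses on the one factor the trial holds fixed and leaves out the factor it manipulates. If dose does not vary, the planned models cannot be fitted in any useful sense. Even if they could, they would not say whether sprouts or DIM change BaP kinetics.

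The team would then have to devise the real analysis later. Several PK parameters, two intervention contrasts and a significance threshold would all be open to choice once results are visible. Section 13 says the findings are meant for journals and for EPA risk models, so a result chosen that way could travel well beyond this study.

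**Working it through.** The documents give no power or precision figure, so there is nothing of the plan's own to reproduce. The check is whether the planned models can be estimated.

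**Inputs.** 7 completers (Section 14); 3 cycles (Section 20); dose d = 50 ng in every cycle (Sections 13, 20 and 24). Records: 7 × 3 = 21.

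**SAP step 1: y = a + b·d.** The design matrix has a column of 1s and a column of 50s, and the second is 50 times the first. Rank is 1 of 2, Σ(d − mean d)² = 0 and det(X′X) = 0. The slope b and its t-test do not exist.

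**SAP step 2.** This cannot be reached, because step 1 cannot show a change with dose. If it were run anyway:

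- Line through the origin: k = Σdy/Σd² = (mean y)/50, which is only the mean rescaled.
- Michaelis-Menten: y = Vmax·d/(K + d). The derivatives are d/(K + d) for Vmax and −Vmax·d/(K + d)² for K. Both are constant when d is constant, so the Jacobian has rank 1 of 2. Any K fits equally well with a matching Vmax. In a simulated data set the residual sum of squares was 0.5775 for K = 1, 50 and 1000, the same as for the line.
- BIC: equal fit and one extra parameter, so the line wins by ln(21) = 3.04 whatever the data show.

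**What a within-participant model gives.** Take participant as fixed effects (7 columns) plus condition (2 columns).

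- Rank 9 of 9; residual df 21 − 9 = 12.
- Standard error of sprouts − alone, or DIM − alone, on the log scale: √(2/7) = 0.535 residual SD.
- 95% half-width: 2.179 × 0.535 = 1.165 residual SD. The documents give no within-participant CV. For assumed CVs of 20%, 30% and 50% the residual SD is √ln(1 + CV²) = 0.198, 0.294 and 0.472, and the interval runs from the ratio divided by, to the ratio multiplied by, about 1.26, 1.41 and 1.73.

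**Period terms.**

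| Added term | Rank | Contrasts with BaP alone |
|---|---|---|
| Cycle 2 versus 3, order split 4/3 | 10 of 10, 11 df | SE 0.536 |
| same, split 5/2 | 10 of 10 | SE 0.549 |
| same, split 6/1 | 10 of 10 | SE 0.600 |
| same, split 7/0 | 9 of 10 | not estimable |
| Three-level period (4/3) | 10 of 11 | not estimable |

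The last row fails because BaP alone is always Cycle 1 or comes from an earlier study.

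**Excluding imported BaP-only cycles.** With m participants keeping their own BaP-only cycle, the variance is 3/(2m) + 1/14 in units of residual variance.

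| Dropped | m | SE (residual SD) |
|---|---|---|
| 0 | 7 | 0.535 |
| 2 | 5 | 0.609 |
| 4 | 3 | 0.756 |
| 6 | 1 | 1.254 |
| 7 | 0 | not estimable |

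**The case against.** **The SAP does not name its data set.** Protocol 8233 is titled a dose-response study, and another related protocol used 46 ng, so a pooled dose regression could be estimated. But no pooling is planned in either document, and a BaP dose slope would still not be a sprouts or DIM contrast.

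**Comparing slopes might mean comparing conditions, or capsule error might supply dose spread.** No condition is named, and there is no slope at one dose. A tolerance of 10% around 50 ng (45 to 55 ng) is incidental error, with no measured value for the capsule each participant swallowed.

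**The protocol says it is not powered to generalise** (Section 15, item 4a), so formal error control may be more than it needs. That bears on precision and on how results are labelled. It does not excuse an analysis that cannot address the hypothesis.

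**The PBPK model is a benchmark.** Section 13 refers to its predictions but gives no criterion for agreement, so it does not fill the gap.

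**The grant document, not seen here, may describe the analysis.** That is possible, and the finding is limited to the protocol and SAP.

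Four points stand as refinements. The cycle-2-versus-3 term works only if both orders occur. A log-ratio model does not suit every parameter; time to peak is read from a fixed sampling grid. Elimination could also be defined from the complete 48-hour urine collection. The SAP should say how the PBPK predictions will be compared.

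**Conclusion.** The concern holds, with high confidence, and must be fixed. With 21 records at 50 ng the SAP's slope test has rank 1 of 2 and cannot be computed, its second step cannot be reached, and neither document specifies a comparison of the three conditions. The stated hypothesis therefore has no planned estimate, interval or test.

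The dose models' failure rests on the analysis set being this trial's own cycles at nominal dose, which is all the documents describe. The missing comparison does not depend on that. The precision figures for the replacement assume 7 complete participants, and the 0.536 also assumes a 4/3 order split. The number of imported BaP-only cycles is not stated, so the sensitivity figures are a range.

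**What to change.** Replace the dose-regression, Michaelis-Menten and BIC text. If a pooled dose analysis with another protocol is intended, describe it separately and name its data. The new text should:

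1. Fit, for each suitable log-transformed PK parameter, a model with participant and condition (alone, sprouts, DIM), and report sprouts/alone and DIM/alone geometric mean ratios with 95% intervals. Give a separate paired method for parameters such as time to peak.
2. Name one primary elimination parameter, fully defined. The hypothesis wording points to the plasma elimination rate constant, but the sponsor should choose and justify it.
3. Control error over the two primary contrasts, for example by Holm; unadjusted, two independent tests at 0.05 give 1 − 0.95² = 0.0975. Label all other parameters exploratory.
4. Not fit a three-level period effect. At most add a cycle-2-versus-3 term (−0.5/+0.5, and 0 for BaP alone), only if both orders occur.
5. State that contrasts with BaP alone assume no time trend, which this design cannot check.
6. Report how many BaP-only cycles come from 8233 or 8554, with a sensitivity analysis excluding them.
7. Say how agreement with the PBPK predictions will be judged, or call it descriptive.
8. If data have been seen, as the SAP's past tense may suggest, state that these choices are post hoc.

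The cost is SAP text only: no new visits, samples or participants. The rewrite does not remove the confounding of BaP alone with time order, and it cannot make a choice prespecified if results are already known.
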